Title: Evaluate the Efficacy of Two Advanced Skin Treatment Regimens in Treating Incontinence-associated Dermatitis: Cluster Randomization Study

Study protocol

Study design

An open-label, cluster randomized, three-group, prospective study will be adopted. Cluster randomization will be used to allocate the selected wards to the experimental or control group for ease of operation (Hemming, Eldridge, Forbes, Weijer, amp; Taljaard, 2017), avoiding confusion on the treatment regimens and cross-contamination of subjects (Sedgwick, 2012). The randomized code for the nursing units will be generated using www.randomizer.org as Treatment 1 or Treatment 2 or Control. Blinding is not possible as the treatment products cannot be “masked”. A purposive sampling on inpatients with IAD will be recruited into the study upon consent. The inclusion and exclusion criteria are as listed in K1 amp; K2. The participants will automatically follow the randomization code selected (implied either control or treatment arm) by the nursing unit he is being admitted.

Study materials

Control

The control regimen for IAD is the current standard of care implemented by the organizations participating in the study. The control regime are combination of treatment - varied practices currently for the treatment of IAD – including the use of potassium permanganate, barrier cream or zinc oxide with skin wipes or soap and water for cleaning

Treatment products

The recommended treatment for IAD should include a structured skin care regimen containing a skin cleanser and a skin protectant. The chemical components recommended as protectants should contain either zinc-based, petrolatum-based, dimethicone-based, or an acrylic polymer. The four preselected products for review are: (1) Conveen easi cleanse and Coloplast Conveen critic barrier (2) 3M No rinse cleanser and 3M Caviton No string Barrier Film (3) 3M No rinse cleaner and 3M Caviton Advanced Skin Protectant(4) Smith and Nephew Moisturizing cleanser and Secura EP cream 30%

Study process

Screening/Recruitment

1. When a potential candidate is identified, the research team members will be activated.
2. Eligible participants from the cluster randomized nursing units will be screened. If they meet the inclusion/exclusion criteria, the PI / co-I will be approached the participants face-to-face.
3. The study information will be explained to them at their individual bedside cubicles or a quiet corner of the nursing unit for semi-ambulant participants. Time will be given for consideration to the study. All questions asked will be answered. Upon verbal agreement, the consent will be taken using the appropriate ICFs attached.
4. The nurse-in-charge/doctor-in-charge of the patient will be notified of the participant's agreement to the study.

Study day process

5. Arrangement will be made with the nurse-in-charge to synchronize the daily skin assessments with the study assessment to avoid unnecessary exposure.
6. An initial baseline assessment (Day 0) will be conduct on the participant's buttocks, posterior aspect of thigh and perineal region. The subject will be placed on a lateral comfortable position.
7. Observations made will include the amount and extent of denudement, exudate level, redness, signs of infection and the skin condition.
8. A baseline photo will be taken prior treatment.
9. Concealed treatment codes placed in a sealed opaque envelope will be used for randomizing the cluster. Each nursing units will be asked to draw the sealed envelope. With the sealed envelopes contained numbers 1 to 3 where 1 = Standard of care (control), 2 = Treatment regimen 1, 3 = Treatment regime 2. Each draw will determine the allotted treatment for the study site to adopt.
10. The treatment products will be issued to the nurse for application.
11. The treatment regimens will be applied as per manufacturer's recommendation.
12. Patients will be followed up three times a week for a maximum of 21 days, or until the IAD has healed or discharged from the study site.
13. Each review (including baseline assessment), photos will be taken to document the extent of the IAD over the buttocks and/or thighs and/ or perineal region.
14. All assessments will be made using IADS-D and GLOBIAD tool. Permissions to use the assessment tool has been given.
15. On Day 3, 5 and 7, an assessment will be made to the skin appearance if the IAD has not resolved.
16. Patients on treatment regimens will be identified using visual cue - different flower icons. Patients on control regimens will be treated as per hospital policy on data management
17. All collected data will be entered into the CRF.
18. Upon completion of the data collection, the data will be transcribed into EXCEL and validated independently by two different assigned persons.
19. The validated data in EXCEL will be imported into SPSS and R for data analysis on a later date.

Data collection

Baseline parameters and other outcome measures that will be collected include the pain scores, classification of IAD and healing rates, episodes of incontinence, deterioration to PI or development of other adverse events (Kon et al., 2017) will be collected based on the case record form. Subsequently, 4 more assessments will be made on the participants on the progress of the IAD following treatment(s)/control regimens.

Data Analysis plan

All data will be entered into a Microsoft Office Excel 2013 and independently verified for accuracy of the transcription. The data will then be imported into Statistical Package for the Social Sciences (SPSS) IBM Version 24 and R for analysis and coding. Descriptive analysis including means and standard deviations or medians and interquartile ranges for the numerical variables and frequencies for categorical variables will be used to describe the study sample characteristics. ANOVA will be used to analyse for group differences. The measure of effect (risk difference or mean difference) and a confidence interval or measure of variation will be examined. The intra-cluster correlation coefficient (ICC) will be examined with an ICC of 0.10 used as the acceptable determine for cluster independence during observations (Thomson 2012). Multivariate regression will be used to evaluate the effect of treatment regimens, adjusting for risk factors. A significance level of 0.05 will be used.

We will measure skin characteristics by an independent wound nurse clinician to determine if the photographs reflected any change in skin, size of redness, skin infection or other changes during the follow-up of days 1, 3, 5 and 7 after application of the product. Photographs will be examined to detect any signs of improvement or deterioration in skin condition – redness, maceration of skin and skin erosion (Van de Bussche et al., 2018). A copy of the photograph assessment form is attached. The outcome measures include the pain scores, assessment scores for IAD and healing rates, episodes of incontinence, deterioration to PI or development of other adverse events (Kon et al., 2017).

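### Patients are sampled purposively in open-label wards whose code sets the arm, no arm-unaware recruiter is described, and the plan does not commit to adjusting for baseline severity

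*Combined protocol and SAP*

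**What the plan says.** **Design and allocation.** The Study design section opens with "An open-label, cluster randomized, three-group, prospective study will be adopted" and adds that blinding is not possible. A patient's arm is that of the admitting ward: "The participants will automatically follow the randomization code selected". Patients enter as follows: "A purposive sampling on inpatients with IAD will be recruited into the study upon consent". Eligibility is by criteria K1 and K2, which are not in the supplied text.

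**Recruitment.** Screening/Recruitment item 1 says "When a potential candidate is identified, the research team members will be activated", without saying who does the identifying. Item 2 says "Eligible participants from the cluster randomized nursing units will be screened" and that, if the criteria are met, "the PI / co-I will be approached the participants face-to-face". Consent follows in item 3.

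**Baseline and draw.** Study day process item 6 begins "An initial baseline assessment (Day 0) will be conduct on the" and lists the skin regions examined. Item 8 adds a photograph. Only then does item 9 describe the allocation envelope: "Each nursing units will be asked to draw the sealed envelope". One draw sets the treatment for the site. Item 14 has all assessments made with IADS-D and GLOBIAD. Item 16 marks patients on the treatment regimens with flower icons.

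**Analysis.** The Data Analysis plan compares groups by ANOVA with no covariate mentioned. It then describes a multivariate regression for the treatment effect, adjusted for risk factors that are not listed. It does not say which of the two decides the conclusion.

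**The concern.** Randomising wards balances ward-level factors in expectation. It protects the comparability of the patients within them only if patients enter in the same way whatever the arm. Here a person who knows the ward's code knows the patient's arm before consent, and purposive sampling leaves room to decide who is put forward. The sealed envelope conceals the ward draw; it does nothing for patients selected after it.

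If milder cases were put forward more often in treatment wards, the regimens would look better than they are; if harder cases were, they would look worse. An unadjusted comparison passes that case-mix difference into the result, and more patients or wards would only make the spurious difference more likely to reach significance.

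**Working it through.** **1. Is the arm knowable at recruitment?** Two passages conflict.

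- Item 2 screens patients from units it already calls cluster randomised. On that reading every patient is recruited after the ward's allocation.
- Item 9 comes after consent (item 3), baseline assessment (items 6–7) and photograph (item 8). On that order, patients enrolled before their ward's draw were recruited without knowledge of the arm.

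Because one draw fixes the arm for the whole ward, every later patient there is still recruited with the arm knowable, unless all are enrolled first. The text does not say that they are. The risk survives either reading, but the share of patients exposed to it differs.

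**2. How large could it be?** The documents give no figure to reproduce: no sample size, ward count, SD or correlation. All inputs here are assumed, except that 0.10 is the ICC value the plan mentions as its threshold.

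- Three arms, 50 patients per arm in 5 wards of 10, ICC 0.10, no true effect, total outcome SD 1.
- Baseline severity standard normal, correlation with outcome 0.4–0.6.
- In one arm only, a share s of the most severe fraction p is not approached.

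Baseline shift = s·φ(z₁₋ₚ)/(1 − s·p), and bias = shift × correlation. The range pairs p = 0.10 with correlation 0.4 and p = 0.30 with correlation 0.6.

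The ward-mean variance is 0.10 + 0.90/10 = 0.19. For a ward-level three-group ANOVA (df 2 and 12), the noncentrality is 5 × (2/3) × bias²/0.19.

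| Share skipped | p | Shift (SD) | Correlation | Bias (SD) | False-positive rate |
|---|---|---|---|---|---|
| Half | 0.10 | 0.092 | 0.4 | 0.037 | 5.1% |
| Half | 0.30 | 0.205 | 0.6 | 0.123 | 6.6% |
| All | 0.10 | 0.195 | 0.4 | 0.078 | 5.6% |
| All | 0.30 | 0.497 | 0.6 | 0.298 | 15.3% |

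Size matters: with all skipped, the range is 5.3–9.7% at 30 per arm (3 wards) and 6.5–30.1% at 100 per arm (10 wards).

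**3. What does baseline adjustment achieve?** For a baseline score of assumed reliability 0.7–0.9, the remaining bias is roughly bias × (1 − reliability). With all skipped this runs from 0.078 × 0.1 = 0.008 to 0.298 × 0.3 = 0.089 SD; simulation gave 0.007–0.105.

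**4. Is adjustment at patient level enough?** No. Take correlation 0.5 and reliability 0.8 in the same setting. Adjustment removes 0.5² × 0.8 = 0.20 of the within-ward variance, leaving 0.90 − 0.20 = 0.70, while the ward variance stays at 0.10. The residual ICC is 0.10/0.80 = 0.125 and the design effect is 1 + 9 × 0.125 = 2.125. A three-group test that ignores this rejects with probability of about exp(−5.99/(2 × 2.125)) = 0.244. Simulation agrees: about 24–25%, with or without selection, against about 5–6% when the adjusted analysis is done at ward level.

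**The case against.** Four points can be made for the plan, and each limits what may be claimed.

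- **Purposive may mean only criterion-based.** The phrase refers to inpatients with IAD and is followed at once by the reference to K1 and K2; item 2 then says that those who meet the criteria are approached. A reader might infer that patients are hand-picked by severity. The documents do not say that, and K1/K2 may themselves limit severity. What stands is that neither the word nor item 1 fixes who is put forward for screening.
- **The draw may come later.** A reader might infer from item 2 that all recruitment takes place with the arm known. Item 9's position does not support so firm a reading, and cluster randomised may simply label the participating units. What stands is the exposure of patients enrolled after their ward's draw.
- **Risk factors may include baseline severity.** It would be too strong to say that the plan omits it. The list may be in forms that were not supplied, as may a screening log. What stands is that the supplied text makes no commitment, and that the ANOVA is unadjusted as described.
- **The size is assumed and mostly small.** Partial selection barely moves the error rate. The larger figures need every patient in the top 30% to be missed, in one arm only, with a strong baseline–outcome correlation. Nothing in the documents points to selection of that kind. This objection stands in full.

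**Conclusion.** The concern holds as a design weakness that should be mended, with medium confidence. The combination matters: open-label wards, the arm set by the ward, discretionary sampling, no recruiter stated to be unaware of the arm, and no commitment to adjust for baseline severity. Together these leave the comparability of enrolled patients unprotected.

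A reader might infer that the treatment comparison is biased, or biased in favour of the regimens. The documents support neither; both size and direction are unknown. Within the assumed settings at 50 per arm, the excess over 5% is at most 1.6 percentage points when half of the severe cases are missed. It reaches about 10 points only at the extreme of complete skipping. These figures rest on the assumed ward structure, ICC, correlation and one-arm selection, and they isolate selection by using a ward-level test that the plan does not itself specify.

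**What to change.** 1. Replace purposive sampling with consecutive approach: every inpatient with IAD on a participating ward who meets K1/K2 is approached. Patients should be found by the same case-finding procedure in all arms, for example from the daily skin assessments that item 5 mentions.
2. Keep and report a log of eligible, approached, refused and consented patients by ward and arm.
3. Base the conclusion on a model that adjusts for one pre-specified Day 0 severity score (IADS-D) and accounts for ward clustering, not on the unadjusted ANOVA. A ward-level analysis or a mixed model with a small-sample correction would serve. Patient-level baseline adjustment without clustering is not an adequate substitute.
4. Reconcile items 2 and 9 on when the ward's draw takes place, and state as a limitation that recruitment after the draw is with the arm known.

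The cost is protocol wording, a ward log, a short model specification, some extra screening work and less recruiter discretion. Items 6 and 14 imply that the Day 0 score is already collected. Differential consent and selection on unmeasured factors would remain and should be acknowledged.

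### Two ward-allocation procedures are described, and neither states a restriction on arm sizes or stratification by organisation, although control is each organisation's own usual care

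*Combined protocol and SAP*

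**What the plan says.** Study design sets three arms and allocation by ward: "Cluster randomization will be used to allocate the selected wards to the experimental or control group for ease of operation". The mechanism given there is a web tool: "The randomized code for the nursing units will be generated using www.randomizer.org as Treatment 1 or Treatment 2 or Control".

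Study day process, step 9, gives a different mechanism. "Each nursing units will be asked to draw the sealed envelope", and the contents are described as follows: "With the sealed envelopes contained numbers 1 to 3 where 1 = Standard of care (control), 2 = Treatment regimen 1, 3 = Treatment regime 2". It continues: "Each draw will determine the allotted treatment for the study site to adopt". So the code comes from a website in one place and from a draw in the other, and the unit is the ward or nursing unit in one sentence and the study site in the next.

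Study materials, Control, defines the comparator as "the current standard of care implemented by the organizations participating in the study", in the plural, and says that these practices vary.

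The document does not give the number of wards, the number of organisations, an allocation ratio, the number of envelopes per arm, whether a drawn envelope is put back, or any blocking, matching or stratification. The Data Analysis plan names ANOVA and a regression adjusted for risk factors that it does not list. It names no term for organisation or allocation stratum.

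**The concern.** In a ward-randomised trial, precision depends mainly on the number of wards per arm. An arm with a single ward cannot separate the regimen from that ward's staff, patients and habits, and an empty arm removes a planned comparison. Analysis cannot repair either one.

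Organisation matters here for a specific reason: by the plan's own account, the control is whatever each organisation already does, and this differs. If the draw puts all control wards in one organisation, the comparison rests on that organisation's version of usual care and on its case mix. The regimens would then be compared partly across organisations.

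**Working it through.** The plan states no sample size or ward number, so it has no figure to reproduce. The question is what the described draw allows.

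**Inputs.** Three arms (Study design). Envelopes numbered 1 to 3 and one draw per unit (step 9). More than one organisation (Study materials, Control). Assumed, because not given: the number of wards K, the number of organisations H, equal wards m per organisation, and probability 1/3 per arm.

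**Step 1: arm sizes if draws are independent.** The arm counts (a, b, c) have probability K!/(a! b! c!) / 3^K.

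- P(some arm empty) = 3(2/3)^K − 3(1/3)^K.
- P(some arm has 0 or 1 ward) = 1 − P(all arms have at least 2).
- K = 6: only (2, 2, 2) gives every arm two wards, with probability 90/729 = 12.3%. The complement is 87.7%.
- K = 9: the favourable counts are 1,680 for (3, 3, 3), 6 × 1,260 for orderings of (2, 3, 4) and 3 × 756 for orderings of (2, 2, 5). They sum to 11,508 of 19,683, or 58.5%. The complement is 41.5%.

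| Wards | Some arm empty | Some arm with 0 or 1 ward |
|---|---|---|
| 6 | 25.9% | 87.7% |
| 9 | 7.8% | 41.5% |
| 12 | 2.3% | 16.1% |
| 15 | 0.7% | 5.8% |
| 18 | 0.2% | 2.0% |
| 24 | 0.02% | 0.2% |

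**Step 2: arm sizes if equal numbers of envelopes are drawn without replacement.** Every arm gets at least the whole-number part of K/3. From 6 wards upward that is at least two, so both columns become zero.

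**Step 3: all control wards in one organisation.** With independent draws and q = (2/3)^m, the probability given at least one control ward is H(1 − q)q^(H−1) / (1 − q^H). With balanced but unstratified draws and r = K/3 control wards, it is H × C(m, r) / C(K, r).

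| Organisations × wards | Independent | Balanced, unstratified |
|---|---|---|
| 2 × 3 | 45.7% | 2 × 3/15 = 40.0% |
| 3 × 2 | 36.1% | 3 × 1/15 = 20.0% |
| 3 × 3 | 19.0% | 3 × 1/84 = 3.6% |
| 2 × 6 | 16.1% | 2 × 15/495 = 6.1% |

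Balancing arm sizes therefore reduces this risk but does not remove it.

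**Step 4: balanced draws within organisation.** An organisation with at least three wards then contributes to every arm, so the probability is zero for 2 × 3, 3 × 3 and 2 × 6. For 3 × 2 no organisation can hold all three arms. Pooling them leaves the 20.0% in place.

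**The case against.** The strongest reply is that an opened envelope is naturally used up, so a set numbered 1 to 3 may well be meant as a block of three drawn without replacement. The text allows that reading, and under it the arm-size risk is zero at the ward numbers shown. A reader might infer that the trial has no balancing at all. The documents do not say that. They are silent, and the supportable statement is that no restriction is specified.

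A second reply is that unstratified randomisation is valid in expectation. That is correct. A reader might infer that organisation differences systematically bias the treatment effect, and they do not. What remains is the risk of a chance imbalance in the one allocation that is realised, with the probabilities in Step 3.

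Third, a reader might take the study-site wording in step 9 to mean that whole hospitals are allocated, so that arm and hospital coincide. The documents do not support this as the plan: Study design allocates wards, and step 9 itself has nursing units draw. It is an ambiguity to be reconciled.

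Fourth, the risk factors in the regression are not listed, so an organisation term is unnamed, not shown to be excluded. Adding one without condition is also debatable. In a ward-level analysis of 6 wards in three arms, 6 − 3 = 3 residual degrees of freedom remain (two-sided 5% critical t 3.18). One term for two organisations leaves 2 (4.30), and two terms for three organisations leave 1 (12.7). With few wards, such adjustment can cost more precision than it saves.

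**Conclusion.** The point holds as a gap in the allocation procedure that should be closed before the first draw. Two mechanisms and two names for the allocated unit stand side by side, and neither mechanism states a limit on arm sizes or uses organisation, although the comparator varies by organisation.

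The size depends on facts the plan does not give. For 6 to 24 wards, the chance of an arm with at most one ward runs from 88% down to 0.2% if draws are independent with equal probability, and is zero if equal numbers of envelopes are drawn without replacement. The organisation part does not turn on that question: for the layouts examined, balanced but unstratified draws still put all control wards in one organisation with probability 3.6% to 40%. These figures assume organisations of equal size and ward numbers divisible by three.

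**What to change.** State one procedure, with the ward as the unit, and reconcile Study design with both sentences of step 9. Give the number of wards and organisations.

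- Within each organisation, prepare envelopes in sets of three: one control, one regimen 1, one regimen 2. Shuffle each set, and have all wards draw at the same time without replacement. Where the ward count is not a multiple of three, keep the sets separate so that only the last is part-used.
- Pool organisations with fewer than three wards into a shared stratum. This protects arm sizes but not the spread of control wards among those small organisations, and the report should show that spread.
- In the Data Analysis plan, adjust for the allocation stratum, not for each single-ward organisation, and only where the number of wards leaves enough ward-level degrees of freedom. Fix that condition in advance.

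The cost is slightly more preparation before the first draw, plus one degree of freedom for each stratum beyond the first if it is adjusted for. Drawing at the same time prevents the last ward in a set from foreseeing its allocation. If the envelopes are already prepared this way, one sentence saying so closes the allocation part of the point.

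### A visual identifier is described for the two treatment regimens but not for control, which may add a little differential attention to the comparisons with control (minor)

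*Combined protocol and SAP*

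**What the plan says.** The combined protocol and SAP deals with identification of patients in one place, item 16 under Study day process. For the treatment arms: "Patients on treatment regimens will be identified using visual cue - different flower icons". For control: "Patients on control regimens will be treated as per hospital policy on data management". The item does not say what the icons are for, where they are placed or who sees them.

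The setting comes from Study design: "An open-label, cluster randomized, three-group, prospective study will be adopted". On allocation: "Cluster randomization will be used to allocate the selected wards to the experimental or control group for ease of operation". Each patient takes the arm of the ward to which he or she is admitted. On masking: "Blinding is not possible as the treatment products cannot be" masked. Under items 9 and 10 of Study day process, each nursing unit draws its own allocation and nurses receive the products to apply.

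Other study contacts are written for participants in general, with no distinction by arm. Under Screening/Recruitment, item 4: "The nurse-in-charge/doctor-in-charge of the patient will be notified of the participant's agreement to the study". Item 5 aligns study assessments with the ward's daily skin checks. Item 12: "Patients will be followed up three times a week for a maximum of 21 days", ending sooner on healing or discharge. Item 13 adds photographs at each review.

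**The concern.** In an unmasked trial the arms should differ in the regimen under test and in as little else as possible. Here the text adds something that is not part of either regimen. Study materials describes a regimen as a cleanser together with a protectant; a visual marker is neither.

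The marker would act, if it acts at all, on the people who deliver care. A nurse who sees an icon may check or clean that patient sooner. If healing responds to such attention, part of any advantage over control could come from the marker and not from the products. The documents do not say that healing responds in this way; it is a plausible assumption.

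What is at stake is the interpretation of each regimen's comparison with control. A difference could be credited to the products when a small part of it came from how patients were flagged. The direction, if there is an effect, would favour the treatment regimens.

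**Working it through.** The plan states no event rate, effect size, number of wards or sample size, so there is no figure to reproduce. The check is a reading of the passages against each other.

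**1. What each arm receives, on the current text**

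| Feature | Control | Treatment 1 | Treatment 2 | Source |
|---|---|---|---|---|
| Ward knows its allocation | yes | yes | yes | item 9 |
| Nurse or doctor in charge told of enrolment | yes | yes | yes | item 4 |
| Assessments aligned with ward skin checks | yes | yes | yes | item 5 |
| Regular review and photographs | yes | yes | yes | items 12, 13 |
| Flower icon | none described | yes | yes | item 16 |

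Only the last row differs in a way that is not the regimen itself.

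**2. Which comparisons are exposed.** Code the icon as 0 for control and 1 for each treatment arm. The difference in icon status is:

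- Treatment 1 minus control: 1 − 0 = 1
- Treatment 2 minus control: 1 − 0 = 1
- Treatment 1 minus Treatment 2: 1 − 1 = 0

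The first two comparisons carry the asymmetry and the third does not.

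**3. Whether analysis can remove it.** Let T1 and T2 be indicators for the two treatment arms. As written, icon = T1 + T2 for every participant. An icon term in the regression described under Data Analysis plan would be an exact linear combination of the arm terms, so its effect cannot be estimated separately. Adjusting for patients' risk factors does not change this. The data to be collected include episodes of incontinence, but no measure of how often or how promptly care was given.

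**4. Whether independent assessment helps.** Under Data Analysis plan: "We will measure skin characteristics by an independent wound nurse clinician to determine if the photographs reflected any change in skin". This bears on bias in judging the outcome. If attention changed the care, the skin itself would differ, and an independent reader of photographs would correctly record that difference.

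**5. What the icon adds to existing knowledge.** All participants on a ward share one arm, so the icon is not needed to tell regimens apart within a ward, and it does not reveal the allocation. Its practical effect is to mark out individual participants from other patients on the ward. Control participants are known to staff through items 4, 5, 12 and 13 but have no described marker.

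**The case against.** The strongest case on the other side has four parts.

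- **Location and purpose are not stated.** A reader might picture an icon at the bedside acting as a constant reminder. The documents do not say that. The icon could be on a chart, a product or a record form, where it would prompt much less. This stands, and the point must not rest on a bedside cue.
- **The control sentence is unclear.** It refers to a data-management policy, and the next item concerns entry into the case record form. Item 16 may be about labelling, and it does not expressly rule out an identifier for controls. This also stands. The two sentences do contrast the arms, however, and nothing elsewhere makes identification equal.
- **Little is left for the icon to add.** Staff know the ward's allocation and are told who has enrolled, and control patients get the same notification, reviews and photographs. Most of the performance bias comes from the open-label design, which the plan acknowledges. This stands as a reason to think the effect small. It does not remove the point: knowing the ward's arm is general knowledge, while an icon marks an individual patient, and this part of the bias can be avoided.
- **Equalising changes the control arm.** If the icon does prompt attention, giving it to controls moves them slightly away from usual care. This is a real but small cost, since controls are already enrolled, reviewed and photographed as study patients.

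**Conclusion.** The concern holds as a minor point of conduct. On the current text, identification differs between the treatment arms and control. It may add patient-level differential attention to the open-label bias already present in the two comparisons with control, and the analysis cannot isolate it. This rests on two assumptions: that the icon is visible to the nurses giving care, and that controls have no equivalent marker. Item 16 suggests both but states neither outright.

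The size is unknown and probably small. A reader might try to quantify it, for example by assuming no product effect, 50% of controls healed by Day 7 and a healing rate raised by a factor r. Healing would then be 1 − 0.5^r: 53.3% for r = 1.1 and 59.4% for r = 1.3, or about 3 to 9 points above control. Both inputs are invented, r = 1 gives no difference, and the result only restates the assumption. It is not evidence of a bias of that size.

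Two stronger readings are also not supported. A reader might infer that the trial applies a reminder intervention and that its results against control are therefore confounded; the documents show only an asymmetric identifier, with no stated prompting function and no evidence of an effect on care. A reader might also infer that the whole three-group comparison is affected; Treatment 1 versus Treatment 2 is not.

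**What to change.** Change item 16 so that participants in all three arms, including control, carry an equivalent visual identifier in the same place, with a different flower for each arm. State in the same item what the identifier is for and where it is placed, and reword the control sentence so that it is clear whether it concerns care, labelling or data handling.

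The cost is one more icon design and a short edit. No product, schedule or assessment changes, and the icons keep any role they have in identifying the regimen. The downside is that control care becomes slightly less like everyday usual care. The change removes one source of differential attention; it does not remove the bias inherent in an open-label trial.
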